1.3 Rationale for Study Conduct, Design, and Dose Selection

Study NEOD001-OLE251 is an open-label extension study, designed to allow subjects who completed Study NEOD001-201 to receive active treatment and to evaluate the long-term safety and efficacy of NEOD001 as a single agent in subjects with AL amyloidosis who were previously treated with PCD therapies. The selected dose of NEOD001, 24 mg/kg (dose not to exceed 2500 mg), was used in Study NEOD001-201 and will be continued in this study and the other ongoing studies of NEOD001.

NEOD001 is currently being studied in 3 other ongoing studies. Study NEOD001-201 is a double-blinded, randomized, controlled Phase 2b study designed to evaluate the efficacy and safety of NEOD001 as a single agent in patients with AL amyloidosis whose underlying PCD is stable but who still exhibit significant cardiac impairment. Study NEOD001-CL002 is a double-blinded, randomized, placebo-controlled Phase 3 study in patients with newly diagnosed AL amyloidosis disease who are receiving chemotherapy to treat the underlying PCD. In addition, Study NEOD001-OLE001, an open-label extension study for subjects previously enrolled in the Phase 1/2 Study NEOD001-001, allows subjects to receive NEOD001 and concomitant chemotherapy for treatment of their underlying PCD.

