5.6.1 Allowed Concomitant Medication/Therapy

- Radiation therapy for the treatment of local amyloid deposits
- Concomitant chemotherapy:
 - The Investigator may prescribe chemotherapy as per standard of care
 - Monthly doses of NEOD001 should not be delayed or skipped due to adjustments made to chemotherapy dosing
 - If bortezomib is administered, antiviral prophylaxis is required

- Particular care must be taken to accurately report chemotherapy administration, including missed or delayed doses, and dose reductions
 - Blood samples for local laboratory assessments must be collected per institutional practice prior to administration of chemotherapy
 - Within 3 days before the first day of a new regimen of chemotherapy, conduct an unscheduled laboratory collection (including hematology, chemistry, prothrombin time/international normalized ratio [PT/INR], and partial thromboplastin time [PTT])
 - If chemotherapy is administered on the same day as NEOD001, the chemotherapy must be administered after the NEOD001 observation period and postdose vital sign measurements
 - Medications such as anti-emetics required for prophylaxis of emesis for the subsequent chemotherapy should be given after the ECG has been completed.
- Calcium channel blockers (if on stable dose)
 - Steroids

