2.2. Study Design

2.2.1. Overall Study Design

This is a global, multicenter, Phase 2b, open-label extension study of subjects with AL amyloidosis who completed Study NEOD001-201. Subjects in this study may receive concomitant chemotherapy.

Subject screening will occur during the 28 days prior to the first administration of study drug (i.e., Month 1-Day 1 Visit), which may overlap with the last visit in Study NEOD001-201. If all eligibility requirements are met, the subject will be enrolled and Screening assessments will be completed. Screening assessments are listed in [Table 1](#).

Study visits will occur every 28 days based on scheduling from Month 1-Day 1. A ± 5 -day window is allowed for visits starting after Month 1. Subjects may receive up to 36 infusions of study drug. Subjects who discontinue study drug before the End of Study (EOS) Visit should have an Early Treatment Discontinuation (ETD) Visit 30 (± 5) days after their final administration of study drug.

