6. EXAMINATION OF SUBGROUPS

No prespecified evaluation of subgroups will be performed.

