7.7. Chemotherapy

Chemotherapy regimens may be prescribed as per standard of care at the Investigator's discretion. All chemotherapy recorded on the Prescribed Chemotherapy Regimens and Concomitant Chemotherapy Treatment Medications eCRFs will be listed for OLE Safety Population.

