9.3. Adverse Events

Verbatim terms on the OLE Adverse Event eCRFs will be mapped to PT and SOC using MedDRA version 19.0. AEs will be reported, and severity will be categorized using the Common Terminology Criteria for Adverse Events (CTCAE, Version 4.03).

All AE summaries will be restricted to treatment-emergent adverse events (TEAEs), which are defined as any AE that newly appears, increases in frequency, or worsens in severity following initiation of study drug and up to 30 days after date of last dose or last study visit, whichever is

later. If it cannot be determined whether the AE is treatment emergent due to a partial onset date, then it will be counted as such.

To assess the long-term treatment effects overall and relative to shorter term treatment, TEAE incidence will be summarized separately by the original parent study (NEOD001-201) and OLE study (NEOD001-OLE251) as shown in Table 6. TEAEs collected during original parent study will be summarized by actual treatment subjects received. TEAEs that start on or after the first dose of OLE study will be summarized by treatment group subjects received in parent study. Overall summary will also be presented for NEOD001-OLE251.

Table 6: Treatment Group Schema

NEOD001-201		NEOD001-OLE251		
NEOD001 (N=xx)	Placebo (N=xx)	NEOD001-201 NEOD001 (N=xx)	NEOD001-201 Placebo (N=xx)	Overall (N=xx)

Each AE summary will be presented according to Table 6 for All Treated Subjects. Summaries that are displayed by SOC and PT will be ordered by descending order of NEOD001-OLE251 overall incidence of SOC and PT within each SOC.

- An overall summary of AE incidences will be presented, including the number and percent of subjects with at least one of:
 - Any TEAE
 - TEAE by maximum CTCAE Grade
 - CTCAE Grade ≥ 3 TEAE
 - Serious TEAE
 - Fatal TEAEs (outcome="Fatal" or severity=CTCAE Grade 5)
 - Treatment-related TEAE
 - Treatment-related serious TEAE
 - Treatment-related TEAE of CTCAE \geq Grade 3
 - TEAE leading to infusion interruption
 - TEAE leading to dose reduction
 - TEAE leading to dose being held
 - TEAE leading to prolongation of infusion time (>2.5 hours)
 - Infusion associated TEAE as determined by the Investigator
 - TEAE leading to study drug withdrawal
- Subject incidence of TEAEs by MedDRA SOC and PT
- Subject incidence of serious TEAEs by MedDRA SOC and PT

The following listings will be presented by subject for OLE Safety Population:

- All AEs

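### SAP Table 6 cannot isolate the effect of longer NEOD001 treatment on TEAEs, because its OLE columns mix NEOD001 with and without chemotherapy and no planned summary separates them

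*SAP*

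**What the plan says.** SAP 9.3 gives the TEAE tables an interpretive purpose: "To assess the long-term treatment effects overall and relative to shorter term treatment, TEAE incidence will be summarized separately by the original parent study" and by the OLE. Table 6 has two parent-study columns (NEOD001, placebo) and three OLE columns (former NEOD001, former placebo, overall). For the OLE, "TEAEs that start on or after the first dose of OLE study will be summarized by treatment group subjects received in parent study". A TEAE is "any AE that newly appears, increases in frequency, or worsens in severity following initiation of study drug", so cause plays no part in the definition.

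On background treatment, Protocol 1.3 describes the parent study as "designed to evaluate the efficacy and safety of NEOD001 as a single agent in patients with AL amyloidosis whose underlying PCD is stable". For the OLE, SAP 2.2.1 says "Subjects in this study may receive concomitant chemotherapy", and Protocol 5.6.1 says "The Investigator may prescribe chemotherapy as per standard of care".

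On using the chemotherapy data, SAP 7.7 says "All chemotherapy recorded on the Prescribed Chemotherapy Regimens and Concomitant Chemotherapy Treatment Medications eCRFs will be listed for OLE Safety Population", and SAP 6 says "No prespecified evaluation of subgroups will be performed". SAP 10 removes every safety analysis except the AE overview, TEAEs and SAEs.

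**The concern.** The parent-study columns are the SAP's own shorter-term comparator. For the comparison to speak to duration of NEOD001 treatment, the columns should differ mainly in duration. The OLE columns also contain whatever chemotherapy investigators prescribe, and the toxicity of that chemotherapy qualifies as treatment-emergent if it starts after the first OLE dose. A higher OLE percentage for, say, serious TEAEs or a neuropathy preferred term could then reflect chemotherapy, longer NEOD001 exposure, longer observation, or a mixture. The tables give the reader no means of telling these apart.

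Long-term safety is part of the study's single stated objective. After SAP 10 no other summary of safety outcomes can help, because laboratory, ECG and vital-sign data are listed only. Protocol 5.6.1 asks for particular care in recording chemotherapy doses, so the information needed is collected but not used in any table.

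**Working it through.** The documents give no figure to reproduce: Table 6 is a shell with N=xx, and sample size is not applicable. The check sets the passages side by side and then does illustrative arithmetic.

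**1. Which rows are exposed**

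| Output in SAP 9.3 | Depends on attributed cause? | Open to chemotherapy toxicity? |
|---|---|---|
| Any TEAE, maximum grade, Grade 3 or higher, serious, fatal, study drug withdrawal | No | Yes |
| SOC/PT table, all TEAEs | No | Yes |
| SOC/PT table, serious TEAEs | No | Yes |
| Treatment-related; related serious; related Grade 3 or higher | Yes, investigator | Partly protected |

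The protection in the last row comes from Protocol 7.3, which lets an event typical of a concomitant drug be called not related. That is an open-label judgement, and neither SOC/PT table has a related-only version.

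**2. How large the shift could be (assumptions only)**

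Suppose longer NEOD001 treatment has no effect. Let b be the background incidence, c the share of OLE subjects who start chemotherapy, and d the added incidence in those subjects. Then OLE incidence = b + c × d, and the shift is c × d. With b = 20%:

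| c | d = 20 points | d = 40 points |
|---|---|---|
| 0% | 20% (shift 0) | 20% (shift 0) |
| 10% | 22% (shift 2) | 24% (shift 4) |
| 25% | 25% (shift 5) | 30% (shift 10) |
| 50% | 30% (shift 10) | 40% (shift 20) |

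None of b, c and d comes from the documents. The table also assumes no chemotherapy toxicity in the parent columns. Any there would shrink the contrast.

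**3. What else moves the same comparison**

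*Observation time.* SAP 4.6.1 shows a parent schedule reaching a Month 12 infusion, and SAP 2.2.1 allows up to 36 OLE infusions. At 28-day spacing, 12 infusions span 11 × 28 + 1 = 309 days and 36 span 35 × 28 + 1 = 981 days. Adding 30 days of follow-up to each, the ratio is r = (981 + 30) / (309 + 30) = 1011 / 339 = 2.98. At an unchanged constant hazard, crude incidence becomes 1 − (1 − b)^r:

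- b = 10% gives 27.0%
- b = 20% gives 48.6%, a shift of 28.6 points
- b = 40% gives 78.2%

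For b = 20% this exceeds every chemotherapy shift in step 2. It is an upper case, because SAP 10 records that the programme was discontinued and actual OLE exposure may be much shorter. If OLE observation were shorter than parent observation (r below 1), the same formula would give an OLE incidence below b.

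*Selection.* Protocol 4.1 admits only subjects who completed the parent End of Study Visit. SAP 9 presents TEAEs for All Treated Subjects, a population that SAP 5 does not define. If it means everyone dosed in each study, the parent columns include non-completers whom the OLE columns cannot contain. That selection may lower OLE incidence.

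**The case against.** The strongest reply has four parts.

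- *The display is descriptive.* SAP 9 plans no inferential safety comparison, and nowhere does the SAP say that an OLE-minus-parent difference is harm from NEOD001. This is true and limits the seriousness of the point. It does not remove it, because SAP 9.3 still gives the comparison a purpose that the columns cannot serve.
- *Causality rows and listings exist.* Three overview rows count only related events, and by-subject AE and chemotherapy listings allow case-by-case review. This also stands, but the remaining all-causality rows and both SOC/PT tables are untouched, and a listing does not give an incidence.
- *There is a contrast inside the OLE.* Former NEOD001 against former placebo compares longer with shorter cumulative exposure under the same chemotherapy rules, without relying on the parent study. This is a real strength of Table 6. Uptake could still differ between the two groups, and no table reports it.
- *The parent study is largely out of sight.* A reader might infer from the words single agent that the parent columns contain no chemotherapy and that its toxicity appears in the OLE columns alone. The documents do not support that. Protocol 1.3 applies the same words to this OLE, where chemotherapy is allowed, so the phrase does not show that chemotherapy was barred. The parent study's concomitant-therapy rules are not given here.

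**Conclusion.** The point holds in a limited form. In the all-causality rows and the two SOC/PT tables, Table 6 cannot attribute a difference between OLE and parent incidence to longer NEOD001 treatment, because chemotherapy is allowed in the OLE and separated nowhere.

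The chemotherapy shift of 2 to 20 points rests entirely on assumed uptake and assumed excess risk, and is zero if no subject starts chemotherapy. A reader might go further and conclude that the table counts chemotherapy toxicity as NEOD001 harm, that the net bias is upward, or that it concentrates in severe events because those given chemotherapy are relapsing. None of these is established. Observation time can push either way, completer selection may push down, and Protocol 5.6.1 refers only to standard of care, with no relapse trigger.

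This is a worthwhile, inexpensive improvement to a descriptive display. It does not invalidate the safety analysis.

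**What to change.** In SAP 9.3 and Table 6:

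1. Keep the all-OLE columns as the main display and head them *NEOD001 with or without chemotherapy*.
2. Report how many subjects started on-study chemotherapy, by parent arm and overall, with the same count for the parent study if available.
3. Add supportive OLE columns for TEAEs with onset before, and on or after, the first on-study chemotherapy dose. Subjects who never start contribute to the first column only.
4. Give exposure-adjusted rates (events or subjects with events per person-year of AE observation) for the parent, all-OLE, pre-chemotherapy and post-chemotherapy columns, since crude percentages over unequal follow-up are not comparable. The person-years in SAP 9.1 run from first to last dose. They need adapting to the TEAE window, which extends to 30 days after the last dose or the last visit, whichever is later. Parent time should stop at the first OLE dose.
5. Do not rest the long-term conclusion on the pre-chemotherapy columns alone. Cutting follow-up at chemotherapy start drops late events and would lower crude percentages, so read these columns beside the all-OLE columns and state that the cut may be informative.

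Separately, the single-agent description of this OLE in Protocol 1.3 and the chemotherapy allowance in 5.6.1 must be reconciled.

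The tables need SAP wording, one derived date per subject from existing chemotherapy eCRFs, and a few extra columns. They need no new data and no protocol amendment. The drawback is shorter, possibly informatively cut follow-up in the pre-chemotherapy columns.

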9.4. Clinical Laboratory Evaluations

Laboratory parameters include serum chemistry, hematology and coagulation.

All clinical laboratory data will be presented in by-subject data listings using standard international (SI) system of units. In addition, separate listings will be presented for any subject with a post-baseline CTCAE grade 3 or 4 laboratory value, or with a post-baseline value outside the normal range where CTCAE criteria cannot be applied to an analyte.

The following normal ranges will be used where not provided in the central laboratory data:

- INR Upper Limit of Normal (ULN) = 1.1
- eGFR LLN = 90 mL/min/1.73m²

9.4.1. Pregnancy Testing and Urinalysis Dipstick

Pregnancy test results and urinalysis dipstick results will be provided in a by-subject data listing.

9.5. Weight and BMI

Weight (kg), BMI (kg/m²), and mBMI (kg/m² g/L), defined as a subject’s weight (kg) ÷ subjects squared height (meters) × serum albumin (g/L), will be provided in a by-subject data listing.

9.6. Vital Signs

Vital sign parameters including temperature (C), systolic and diastolic pressure (mmHg), pulse (beats/min), and respiratory rate (breaths/min) will be presented in a data listing.

9.7. Electrocardiograms

ECGs measurements will be made in triplicate, 5 to 10 minutes apart and assessed by a central reader. ECG parameters include, time between 2 consecutive R waves [RR], PR interval, QRS duration, QT (uncorrected) interval, QT interval corrected by the Bazett’s formula [QTcB], and QT interval corrected by the Fridericia’s formula [QTcF].

Overall interpretation results for ECGs and the investigator interpretation results are collected as normal, abnormal not clinically significant, and abnormal clinically significant. Subjects whose interpretation shifts from normal to abnormal clinically significant or not clinically significant will be listed separately including description of the abnormality and any associated comments.

All ECG results will be presented in by-subject data listings.

9.8. Physical Examination

Physical examination findings entered on the eCRF will be listed.

9.9. Immunogenicity

Immunogenicity of NEOD001 will be assessed by anti-NEOD001 antibody levels. Serum anti-NEOD001 antibody levels will be listed.

10. CHANGES TO PROTOCOL PLANNED ANALYSES

Due to the discontinuation of the NEOD001 program, the following changes were made to any protocol planned analyses:

1. All safety analyses were removed except AE overview, TEAEs and SAEs.
2. The below efficacy analyses were removed:
 - Change from baseline in troponin T
 - Change from baseline in the Short Form-36 Health Survey version 2 (SF-36v2) Mental Component Score (MCS) and the 8 subscales
 - Progression-free survival
 - For renal-evaluable subjects:
 - Time to eGFR:
 - Time to any worsening in CKD Stage
 - Time to 40% reduction in eGFR
 - Time to doubling of creatinine
 - For peripheral neuropathy-evaluable subjects:
 - Peripheral neuropathy best response
 - Peripheral neuropathy response
 - For subjects with painful peripheral neuropathy in Study NEOD001-201 (i.e., baseline Visual Analog Scale – Pain Intensity [VASPI] score >0) change from baseline in the VASPI score
 - For hepatic-evaluable subjects:
 - Hepatic response
 - Hepatic best response from baseline
 - Frequency and duration of hospitalizations over the course of the study
 - Change from baseline in the Kansas City Cardiomyopathy Questionnaire (KCCQ) subscores and overall summary score
 - Time to progression for each organ (cardiac/NT-proBNP, renal, peripheral neuropathy, hepatic) separately and to any organ progression
 - Eastern Cooperative Oncology Group (ECOG) Performance Status and New York Heart Association (NYHA) Class at each visit including any changes from baseline
 - Change from baseline in serum free light chains (sFLCs), serum and 24-hour urine protein electrophoresis (PEP), and serum and urine immunofixation electrophoresis (IFE)
 - Severity of disease-related symptoms including any changes from baseline

12. APPENDICES

APPENDIX 1. HEMATOLOGIC RESPONSE AND PROGRESSION CRITERIA

Response Subcategory	Response Criteria
Complete Response (CR)	Normalization of free light chain levels and ratio, negative serum and urine immunofixation
Very Good Partial Response (VGPR)*	Reduction in the dFLC to <40 mg/L (<4.0 mg/dL)
Partial Response (PR)*	A greater than 50% reduction in the dFLC
No Response (NR)	Less than a PR
Progression	From CR: any detectable monoclonal protein or abnormal free light chain ratio (light chain must double)
	From PR, 50% increase in serum M protein to > 0.5 g/dL or 50% increase in urine M protein to > 200 mg/day (a visible peak must be present) or free light chain increase of 50% to > 10 mg/dL (100 mg/L)

Abbreviations: dFLC = difference between involved and uninvolved free light chains.

*Only applicable for subjects who had dFLC > 50 mg/L (5 mg/dL) prior to treatment.

Source: [Comenzo 2012](#).

APPENDIX 2. ORGAN RESPONSE AND PROGRESSION CRITERIA

Organ	Response	Progression
Heart/Cardiac ^{a,b}	NT-proBNP response (>30% and >300 ng/L decrease in subjects with baseline NT-proBNP \geq 650 ng/L) OR NYHA class response (\geq 2 class decrease in subjects with baseline NYHA class III or IV) ^b	NT-proBNP progression (>30% and >300 ng/L increase) ^c
Renal ^d	\geq 30% decrease in proteinuria or drop of proteinuria below 0.5 g/24 hours in the absence of renal progression	\geq 25% decrease in eGFR
Peripheral Nerve ^e	NIS-LL increase from baseline of <2 points	NIS-LL increase from baseline of \geq 2 points

Abbreviations: ALP = alkaline phosphatase; eGFR = estimated glomerular filtration rate; NIS-LL = Neuropathy Impairment Score–Lower Limbs; NT-proBNP = N-terminal pro brain natriuretic peptide; NYHA = New York Heart Association.

a Modified from Table 2 in [Comenzo 2012](#).

b NYHA class not considered for primary efficacy endpoint analyses.

c Subjects with progressively worsening renal function cannot be scored for NT-proBNP progression.

d [Palladini 2014](#).

e [Coelho 2012](#).

APPENDIX 3. EASTERN COOPERATIVE ONCOLOGY GROUP (ECOG) PERFORMANCE STATUS

Grade	Eastern Cooperative Oncology Group
0	Fully active, able to carry on all pre-disease performance without restriction
1	Restricted in physically strenuous activity but ambulatory and able to carry out work of a light or sedentary nature, e.g., light house work, office work
2	Ambulatory and capable of all self-care but unable to carry out any work activities. Up and about more than 50% of waking hours.
3	Capable of only limited self-care, confined to bed or chair more than 50% of waking hours.
4	Completely disabled. Cannot carry on any self-care. Totally confined to bed or chair.
5	Dead

Source: [Oken, 1982](#).

APPENDIX 4. NEW YORK HEART ASSOCIATION (NYHA) FUNCTIONAL CLASSIFICATION

NYHA Class	Symptoms
I	No symptoms and no limitation in ordinary physical activity, e.g., shortness of breath when walking, climbing stairs etc.
II	Mild symptoms (mild shortness of breath and/or angina) and slight limitation during ordinary activity.
III	Marked limitation in activity due to symptoms, even during less-than-ordinary activity, e.g., walking short distances (20–100 m). Comfortable only at rest.
IV	Severe limitations. Experiences symptoms even while at rest. Mostly bedbound subjects.

Source: [American Heart Association, 2015](#).

APPENDIX 5. NEUROPATHY IMPAIRMENT SCALE – LOWER LIMBS

Neuropathy Impairment Scale – Lower Limbs (NIS-LL)
NEOD001-201

The NIS-LL is a scoring system graduated from 0 points (the normal finding) to a maximum of 88 points (the absence of all motor, sensory, and reflex activity in the lower extremities). The scale is additive of all deficits (64 potential points for muscle strength, 8 points for reflexes, and 16 points for sensory function) in the lower extremities.

Instructions: Complete each assessment outlined below and assign a score for the right side and for the left side.

Assessment	Right	Left	Sum
Muscle Weakness - Score each assessment as: 0 - normal, 1 - 25% weakened, 2 - 50% weakened, 3 - 75% weakened, 4 - paralysis			
Hip Flexion (iliopsoas)			
Hip Extension (gluteus max.)			
Knee Flexion (biceps femoris)			
Knee Extension (quadriceps)			
Ankle Dorsiflexors (tibialis ant. +)			
Ankle Plantar Flexors (gastroc. soleus)			
Toe Extensors			
Toe Flexors			
Reflexes - Score each assessment as: 0 - normal, 1 – reduced, 2 - absent			
Quadriceps femoris			
Triceps surae/gastroc. soleus			
Sensation: Great Toe (terminal phalanx) - Score each assessment as: 0 - normal, 1 – reduced, 2 - absent			
Touch pressure			
Pinprick			
Vibration			
Joint position			
Total Score: _____			

Source: Dyck PJ, Litchy WJ, Lehman KA, et al. Variables influencing neuropathic endpoints: the Rochester Diabetic Neuropathy Study of Healthy Subjects. *Neurology*. 1995;45(6):1115-21.

Performed by (Print Name): _____

Signature

Date: ____ / ____ / ____
 dd mmm yyyy

